11. STUDY COMMITTEES

11.1 DSMB

The independent DSMB will act in an advisory capacity to the Sponsor to monitor the safety of subjects who participate in this study. The DSMB is governed by a charter which explains the working procedures and responsibilities of the DSMB [38].

11.2 Event Adjudication Committee

The independent Event Adjudication Committee (EAC) will adjudicate all events relating to the study endpoints based on prospectively defined criteria detailed in the EAC charter. EAC members must not be employees of the study Sponsor and consists of, at minimum, 3 qualified members (at least one cardiologist specializing in HF); see EAC charter for further details [39]. The EAC will be blinded to study treatment allocations while adjudicating the events. Endpoint adjudication will occur on an ongoing basis throughout the Blinded Treatment Phase of the study.

11.3 Steering Committee

The independent Steering Committee will advise the Sponsor scientifically as well as monitor trial progress and conduct. The specific areas of focus for the Steering Committee are protocol design, execution, analysis, interpretation, and publication of the DIAMOND study, and any proposed sub-studies.

12. STATISTICAL ANALYSIS

12.1 Statistical Methods

Detailed methodology for summary and statistical analyses of the data collected in this trial will be documented in an SAP. A general description of the planned methods is provided below. Any deviation from the SAP will be noted and explained in the final study report.

12.2 Sample Size and Power Calculations

The sample size of 410 subjects per treatment arm (total of 820 subjects) has been calculated to provide 90% power to detect a difference between the control group (placebo) and the active group (patiromer) on the mean change in K^+ levels from Baseline. This sample size calculation was based upon the following assumptions: alpha level of 5% (2-sided), a difference between group means of 0.116, an SD of 0.5, and a 5% annual rate of loss to follow-up.

12.3 Randomization

Subjects will be randomized to the treatment arms (1:1 assignment) using permuted block randomization stratified by geographic region. Randomization will take place using a centralized list accessed electronically via IWRs on the day of randomization, after randomization eligibility is determined.

12.4 Analysis Sets

12.4.1 Randomized Set

All subjects randomized to study treatment.

12.4.2 Full Analysis Set

The full analysis set consist of all subjects who satisfy the following criteria:

- Randomized to treatment
- Received at least 1 dose of randomized treatment

This set will be used for the evaluation of efficacy.

12.4.3 Safety Set

The safety set (SS) consists of all subjects who have taken at least 1 dose of randomized study medication. The subjects in this group will be analyzed based on the treatment they received with data summarized separately for the Run-in and Blinded Treatment Phases of the study.

12.4.4 Run-in Phase Set

The Run-in Phase Set will consist of subjects that signed informed consent, entered the Run-in Phase, and received patiromer, but were not randomized. This set will be used to summarize safety related events that may be related to patiromer treatment.

12.5 Background and Demographic Characteristics

Demographic and Baseline characteristics will be summarized for the Randomized Set and the Run-in Phase Set.

Summaries of continuous variables will include the mean, SD, SE, median, 25th and 75th percentiles, and the maximum and minimum. Summaries of categorical variables will include counts and percentages.

Listings for demographics and baseline characteristics will be provided.

12.6 Study Medication

The total amount of drug given will be calculated for each subject and will be compared to the amount expected to be given for each subject. Treatment compliance will be calculated for each subject and summarized by treatment group.

12.7 Concomitant Therapy

Concomitant medications (as defined in Section 6.8.4) will be categorized according to a standard dictionary (World Health Organization Drug Dictionary). Counts and percentages of subject use for each medication will be computed and summarized by treatment group. Summaries will be provided for the periods before and after randomized treatment was received.

12.8 Efficacy Evaluations

12.8.1 Primary

The primary analysis will be based upon the mean change in serum K⁺ levels from Baseline and is analyzed by means of an MMRM approach including all available post Baseline data. All analyses will be restricted to serum K⁺ assessments and not substituted by plasma values as they are known to be systematically lower. Central laboratory values and/or local laboratory will be used at all visits, and if both values are present at one visit, then central laboratory values will be used. A Gaussian linear model for repeated measures with treatment, geographic region, sex, baseline T2DM status, and visit as factors, and baseline K⁺ level, baseline eGFR as covariates. The error terms are assumed to follow a multivariate normal distribution with unstructured covariance. Least squares mean changes from Baseline will be reported for both treatment groups with 95% CIs as well as the difference between the least squares group means with 95% CI and p-value testing the null hypothesis of no treatment effect.

Sensitivity analyses for the primary endpoint will be based upon the use of all CV deaths and hospitalizations (i.e., recurrent event analysis) recorded during follow-up using the following methods: will explore changes in treatment effect over follow-up time by including treatment by visit interactions in the above-mentioned model. In addition, sensitivity analyses for the primary endpoint will explore changes in treatment effect over follow-up time by including treatment by visit interactions in the above-mentioned model. In addition, sensitivity analyses accounting for potentially informative missingness will be based upon a Win Ratio approach [4,40].

12.8.2 Key Secondary Endpoints (Hierarchically Ordered)

Secondary efficacy endpoints will be tested sequentially in the order listed below (i.e., fixed-sequence method to preserve the family-wise error rate) and summarized descriptively through the calculation of point estimates by treatment group along with 95% CIs for the treatment differences. The following lists the secondary endpoints and the analysis method to be used:

- Hyperkalemia events: The time to the first event of hyperkalemia with a serum K⁺ value >5.5 mEq/L as per the measured values from the central or local laboratories is analyzed using a Cox proportional hazards regression model. The event probabilities will be estimated using the Aalen-Johansen estimator of the cumulative incidence function accounting for competing events such as death.
- Durable enablement to stay on the MRA target dose (of 50 mg spironolactone or eplerenone): The time to the event of reduction of the MRA dose below target is analyzed using a Cox proportional hazards regression model. The event probabilities will be estimated using Aalen-Johansen estimator of the cumulative incidence function accounting for competing events such as death.

Note: Discontinuation of the target dose for at least 14 days (or less if at the EoS) is required to confirm this endpoint.

- Investigator reported AEs of hyperkalemia (first and recurrent) are analyzed using a negative binomial regression with the logarithm of the individual follow-up time as offset. A joint frailty model of the total (first and recurrent) hyperkalemia events and time to death as terminating event. If all-cause mortality is substantial in number and differential between the treatment groups, then the joint frailty model would become the main analysis approach. Note: For analyses based upon the negative binomial distribution, the subject level count data will be modeled as function of treatment with the natural log of the subject level follow-up time taken into account in the estimation of the event rate.

- Hyperkalemia-related hard outcomes are analyzed using the Win Ratio approach with the following hierarchical components (all assessed during comparable follow-up times):
 1. Time to CV death
 2. Total number of CV hospitalizations
 3. Total number of hyperkalemia toxicity events with serum $K^+ > 6.5$ mEq/L
 4. Total number of hyperkalemia toxicity events with serum $K^+ > 6.0-6.5$ mEq/L
 5. Total number of hyperkalemia toxicity events with serum $K^+ > 5.0-6.0$ mEq/L
- RAASi Use Score which will be analyzed using the Win Ratio approach for each pair of patients at the end of the comparable follow-up period that is appropriate for that pair of patients with the following additive components. Points are accumulated from two components at the respective time for each patient in each comparison:

Component A:

- If during the follow-up (to the respective end of follow-up in the comparison) there was a death, the subject is assigned 0 points
- If during the follow-up (to the respective end of follow-up in the comparison) there was a CV hospitalization, but the subject is alive at the end of that follow-up, the subject is assigned 1 point
- If during the follow-up (to the respective end of follow-up in the comparison) there was no CV hospitalization and the subject is alive at the end of that follow-up, the subject is assigned 2 points

Component B:

Further points are collected for the treatment status at the respective end of follow-up in the comparison:

- For ACEi/ARB/ARNi use: $>50\%$ of the target dose = 2 points
- For ACEi/ARB/ARNi use: >0 and up to 50% of the target dose = 1 point
- For MRA use: $>50\%$ of the target dose = 2 points
- For MRA use: >0 and up to 50% of the target dose = 1 point
- For beta-blocker use: $>50\%$ of the target dose = 2 points

- For beta-blocker use: >0 and up to 50% of the target dose = 1 point

In summary, each subject in each comparison can have 0-8 points (sum of Components A and B) and all subjects are compared using this score at the respective appropriate follow-up time point.

The regression analyses will be adjusted for geographic region as the stratification factor of the randomization and relevant baseline characteristics of the subjects.

12.8.3 Other Secondary Endpoints

The additional endpoints listed below (Other Secondary Endpoints), will also be summarized descriptively by treatment arm in the full analysis set:

- Durable enablement to stay on the target dose of ACE/ARB/ARNi

Note: Discontinuation of the target dose for at least 14 days (or less if at the EoS) is required to confirm this endpoint

- Durable hyperkalemia-free enablement to stay on the MRA target dose (days on 50 mg MRA without presence of hyperkalemia)
- Hyperkalemia toxicity events with serum $K^+ > 6.5$ mEq/L
- Hyperkalemia toxicity events with serum $K^+ > 6.0-6.5$ mEq/L
- Emergency treatment for hyperkalemia (hospitalization or emergency room)
- Total number of hyperkalemia toxicity events with serum $K^+ > 5.0-6.0$ mEq/L
- KCCQ questionnaire - OSS, CSS and TSS
- Investigator reported events of hyperkalemia (recurrent events)
- Proportion of subjects on $\geq 50\%$ of target dose of ACEi, ARB, or ARNi and $\geq 50\%$ of target dose of MRA at the EoS Visit
- Time to first occurrence of CV death or CV hospitalization

12.8.4 Other Endpoints

- CV death
- First and recurrent CV hospitalizations
- First and recurrent HF hospitalizations (or equivalent in outpatient clinic)
- Patient-reported outcome: EQ-5D-5L questionnaire

- Proportion of subjects on any dose of MRA at the EoS Visit
- Proportion of subjects on any dose of ACEi, ARB, or ARNi at the EoS Visit
- Change in proteinuria from Screening
- Change in NT-proBNP from Screening
- Change in high sensitivity troponin from Baseline
- Functional status by NYHA class
- 30-day HF re-hospitalization after a prior HF hospitalization
- HEOR analyses
- Changes in serum K⁺ from Baseline to individual visits

12.8.5 Subgroups of Interest

Descriptive analyses (including the presentation of 95% CIs) will be produced for the subgroups specified below. These descriptive analyses will be summarized graphically through the use of forest plots.

Subgroups to be analyzed include:

- At Screening, hyperkalemic versus normokalemic with a history of hyperkalemia
- Screening use of ARNi (Yes or No)
- Screening use of eplerenone or spironolactone (Yes or No)
- Screening comorbidity:
 - Diabetes mellitus (Yes or No)
 - CKD stage (Stage 3b versus Stages 1–3a, Stage \leq 3a versus Stage \geq 3b, Stage 4 versus Stage $<$ 4)
 - NYHA Class (II versus III–IV)
- Region (US versus Non-US)

Note: Depending on actual subject recruitment, additional comparisons between other regions, e.g., Latin America, Western Europe, Eastern Europe, will be defined in the SAP

- Gender (male or female)

- Age (age group categories will be defined prior to unblinding)
- Race/ethnicity (limited to racial/ethnic subgroups that comprise 20% or more of the study population)
- Median NT-proBNP at Screening

12.9 Safety Evaluations

The following safety variables will be summarized using the safety set:

- AEs and SAEs (coded using Medical Dictionary for Regulatory Activities (MedDRA); see Study Manual for MedDRA version), including all-cause mortality
- Slope of eGFR change during the study will be estimated and compared between treatment groups using a repeated measures analysis with time treated as a continuous variable
- Decline in eGFR >50% or ESRD, renal death, or need for dialysis
- Laboratory parameters other than those defined as efficacy endpoints

AE summaries will be provided separately for: (1) AEs with start date on or after first dose date during the Run-in Phase and on or before the date of randomization; and (2) AEs with start date on the day after randomization. Summaries will consist of counts (%) by system organ class (SOC), preferred term (PT) and severity in the Run-in Phase, and by SOC, PT, severity, and treatment in the blinded withdrawal phase. The following types of AEs will be summarized:

- All treatment-emergent adverse events (TEAEs)
- TEAEs related to study medication (patiromer/placebo) and to RAASI
- TEAEs leading to study medication discontinuation (patiromer/placebo) and to RAASI discontinuation
- SAEs

A listing of AEs will be provided, to include verbatim term, PT, SOC, intensity/severity, relationship to patiromer/placebo, and to RAASI, whether serious, onset/end date, action taken and outcome of event.

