10.5 Recording and Reporting

10.5.1 Persistent or Recurrent Adverse Events

AEs that extend continuously, without resolution, between trial assessments will only be recorded once in the eCRF. A new event will be documented each time the intensity of an event has changed.

AEs that resolve and subsequently recur will have each recurrence recorded separately in the eCRF.

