If a laboratory abnormality meeting the above criteria is not a sign of a disease or syndrome, the abnormality itself should be recorded in the eCRF, along with a descriptor indicating if the test result is above or below the normal range (e.g., "elevated K⁺," as opposed to "abnormal K⁺").

If the laboratory abnormality can be characterized by a precise clinical term per standard definitions, the clinical term should be recorded as the AE, for example, hypercalcemia or hypoglycemia. Observations of the same laboratory abnormality from visit to visit should not be repeatedly recorded in the eCRF unless the etiology changes. The initial severity of the event should be recorded, and the severity or seriousness should be updated any time the event worsens.

All pathological laboratory findings/values diagnosed throughout the treatment period should be reviewed by the Investigator to provide a final clinical assessment in view of the dynamic of laboratory changes/abnormalities.

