10.7.2 Serious Adverse Event Reporting

The SAE reporting period begins at the time the ICF is signed by the subject. The SAE reporting period ends 2 weeks following the EoS or until 2 weeks after last study drug administration, whichever is longer. If the final Follow-up Visit is conducted as a telephone call rather than a formal visit, the Investigator must report any SAEs that occur during this period.

The occurrence of an SAE must be immediately reported to the Sponsor (or its delegate, e.g., CRO) within 24 hours of awareness by facsimile, email, or telephone/via EDC system. This includes all SAEs (independent of relationship to study treatment).

A death occurring during the study or which comes to the attention of the Investigator within 2 weeks after the EoS or until 2 weeks after the last study drug administration, whichever is longer, whether considered treatment-related or not, must be reported to the CRO/Sponsor.

Any SAE considered to have a causal relationship (i.e., related) to the investigational product and discovered by the Investigator at any time after the study should be reported. A rationale for the assessment of a causal relationship must be provided by the Investigator. Any safety information that is obtained after database lock of the clinical database will be documented in the safety database and implications for handling the data in the clinical database assessed on an individual case basis.

The onset date of the SAE is defined as the date the signs and symptoms/diagnosis became serious (i.e., met at least one of the criteria for seriousness; see Section 10.7.1). If the subject experiences an AE and it progresses into an SAE, a new SAE should be recorded. The original AE stop date should be the same as the start date of the SAE. However, when the SAE resolves and the pre-existing AE is still ongoing, this should be recorded as a new AE. The resolution date of an SAE is defined as when the symptoms resolve, or the event is considered chronic (e.g., sequelae) or stable, and/or if the seriousness criteria are no longer applicable.

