2.17.1 Adverse Events

Adverse events (AEs) and serious adverse events (SAEs) coded using MedDRA (MedDRA version 23.0 or an updated version), including all-cause mortality, will be summarized descriptively.

AE summaries will be provided separately for the Run-in Phase and the Blinded Treatment Phase in the SS.

AE summaries will consist of counts (%) by MedDRA SOC and PT in the Run-in Phase, and by MedDRA SOC, PT and treatment arm in the Treatment Phase. The following types of AEs will be summarized:

- All treatment emergent adverse events (TEAEs)
- TEAEs by severity
- TEAEs related to study medication (patiromer/placebo)
- TEAEs leading to study medication discontinuation (patiromer/placebo)
- SAEs
- SAEs related to study medication (patiromer/placebo)

AE summaries will also be presented in the Run-in Phase Set.

A listing of AEs will be provided, to include verbatim term, preferred term (PT), system organ class (SOC), intensity/severity, relationship to patiromer/placebo, whether serious, onset/end date, action taken and outcome of event.

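### Blinded-phase adverse events are allocated by record start date, and easing opens a new record, so a Run-in patiromer AE that eases after the switch to placebo counts as a placebo event

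*Protocol*

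**What the plan says.** **Allocation to phase.** Protocol 12.9 defines two AE summaries. The Run-in summary takes "AEs with start date on or after first dose date during the Run-in Phase and on or before the date of randomization". The blinded-phase summary takes "AEs with start date on the day after randomization", which I read as that day or later. SAP 2.17.1 adds only that "AE summaries will be provided separately for the Run-in Phase and the Blinded Treatment Phase in the SS".

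**Recording of symptomatic AEs.** Protocol 10.5.1 begins with "AEs that extend continuously, without resolution, between trial assessments will only be recorded once in the eCRF", but its next sentence makes an exception: "A new event will be documented each time the intensity of an event has changed". Protocol 10.4.1 states the same exception. Neither limits it to worsening. Protocol 10.7.2 has a parallel rule for serious events: "when the SAE resolves and the pre-existing AE is still ongoing, this should be recorded as a new AE".

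**Recording of laboratory and other abnormalities.** Protocol 10.5.4 sets a different rule: "Observations of the same laboratory abnormality from visit to visit should not be repeatedly recorded in the eCRF unless the etiology changes", and "the severity or seriousness should be updated any time the event worsens". Protocol 10.5.5 repeats it for vital signs, ECGs and other findings.

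**Treatment emergence.** Neither document gives a general definition. SAP 2.14.1 covers onset on the first dosing date, without saying whether that is the Run-in or the blinded dose. SAP Appendix A covers AEs with missing or partial dates.

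**The concern.** In a randomized-withdrawal design, both arms enter the blinded phase with side effects acquired on active drug. An allocation rule based on start dates is safe only if a new start date means a new or worse event. Here it can also mean improvement. The arm in which patiromer side effects should ease is placebo, so improvement caused by stopping the drug is tabulated as a placebo event.

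At stake is the trial's only randomized safety comparison, and mainly its gastrointestinal terms, where AE records are the principal evidence. Protocol 10.4.2 lists improvement on withdrawal among the features of a related event, so such a record may also reach the table of related events under placebo.

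**Working it through.** The plan states no figure on this point, so the check traces the rules and then illustrates the size.

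**Step 1: the rules applied to one case.** Moderate constipation starts in Run-in and is ongoing at Day 1.

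| Course after Day 1 | New record under 10.4.1/10.5.1? | Blinded-phase count under 12.9 |
|---|---|---|
| Placebo, eases to mild on Day 5 | Yes, starts Day 5 | 1, placebo |
| Patiromer, stays moderate | No | 0 |
| Patiromer, eases to mild | Yes | 1, patiromer |
| Either arm, resolves without an intermediate grade | No | 0 |
| Either arm, worsens to severe | Yes | 1, as it should be |

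A mild AE has no lower grade to step down to, so its resolution opens no record. The first two rows give placebo 1, patiromer 0 for a side effect that began on patiromer in both subjects.

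**Step 2: search for a rule that prevents this.** SAP 2.14.1 works from onset date. SAP 2.17.1 splits by phase. SAP Appendix A imputes dates. SAP Section 3 lists no change to the allocation rule. None links successive records of one AE or requires worsening over the state at randomization.

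**Step 3: inputs for size.**
- From the documents: N = 410 per arm (Protocol 12.2). Rates r from earlier patiromer trials (Protocol 7.2) are constipation 5.9%, diarrhea 4.9%, nausea 2.1% and flatulence 2.1%. Their sum is 15.0% if the terms do not overlap.
- Assumed, because the documents give nothing: share ongoing at Day 1, o = 20-50%; share of those moderate or severe, m = 20-40%; share of those that step down a grade, s = 30-50%.

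**Step 4: gross number of extra placebo subjects = N × r × o × m × s.**
- Low: 410 × 0.150 × 0.20 × 0.20 × 0.30 = 0.74 subjects; 0.74/410 = 0.2 points.
- High: 410 × 0.150 × 0.50 × 0.40 × 0.50 = 6.15 subjects; 6.15/410 = 1.5 points.
- Constipation alone: 410 × 0.059 × 0.012 = 0.29 to 410 × 0.059 × 0.10 = 2.42 subjects, or 0.07 to 0.59 points against a rate of 5.9%.
- Wider assumptions for constipation (o = 25-75%, m = 20-40%, s = 25-100%) give 0.30 to 7.26 subjects, or 0.07 to 1.77 points. The top requires every ongoing moderate or severe case to pass through a lower grade before resolving.

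**Step 5: net effect on the arm difference.** Easing on patiromer also opens records, so the net is N × r × o × m × (s on placebo − s on patiromer). With o = 50%, m = 40%, and s = 50% on placebo against 30% on patiromer: 410 × 0.150 × 0.50 × 0.40 × 0.20 = 2.46 subjects, 0.6 points. If easing were equally common in both arms, both counts would be inflated but the difference would not shift.

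**Step 6: laboratory and other abnormalities.** Protocol 10.4.1 and 10.5.1 call for a new event at each intensity change; 10.5.4 and 10.5.5 call for one record, updated. A hypomagnesemia that worsens after randomization gets a blinded-phase start date under the first pair and keeps its Run-in date under the second. The documents do not say which governs.

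**The case against.** The best defence is that the effect is small and traceable. Protocol 7.2 describes gastrointestinal reactions as mostly mild or moderate, so few can step down. A record created by easing carries the lower grade. SAP 2.17 makes safety analyses descriptive, and the listings show onset, end, severity and outcome, so a reader could identify continuations. The rates in 7.2 come from other trials, and subjects who tolerated patiromer poorly may not have reached randomization. All of this stands and limits the size. It does not remove the artefact, because a listing does not change the counts in the tables.

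Stronger readings are tempting, but the documents do not support them:
- **A larger count.** Omitting the moderate-or-severe share gives 410 × 0.150 × 0.06 = 3.7 to 410 × 0.150 × 0.25 = 15.4 subjects. That lets mild AEs step down, which they cannot. Comparing a four-term sum with single-term rates also overstates its importance.
- **A reversed sign.** Nothing shows this for any term. Narrowing is what the mechanism supports.
- **A hidden magnesium effect.** SAP 2.17.2 tabulates central laboratory values and change from baseline by arm, and the incidence of magnesium below 1.4, 1.2 and 1.0 mg/dL. These do not depend on AE start dates.
- **Laboratory worsening lost from the patiromer arm.** This assumes that 10.5.4 overrides 10.5.1. The text leaves the conflict open.
- **Step-down from serious events as a route for gastrointestinal AEs.** Protocol 7.2 reports no serious gastrointestinal reactions, so this route is marginal for them.

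**Conclusion.** The concern holds for symptomatic AEs. Followed as written, the recording and allocation rules count the easing of a Run-in patiromer side effect as a new blinded-phase event, and no SAP rule corrects it. That such a record is a blinded-phase TEAE is the natural reading of the start-date rule, since no general definition is given.

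The expected direction is a narrower patiromer-placebo difference in gastrointestinal AEs, provided that easing is more common after withdrawal than on continued drug. The gross size is about 0.7 to 6 of 410 placebo subjects, 0.2 to 1.5 points over four terms, under the three assumed shares; the net is smaller by whatever easing occurs on patiromer. For laboratory and other abnormalities the finding is an unreconciled conflict between recording rules, with no established direction of bias.

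**What to change.** **In Protocol 12.9 and SAP 2.17.1:** link contiguous records with the same preferred term as one AE. Count an AE already present at the first blinded dose as a blinded-phase TEAE only if a later record shows higher intensity than at that dose, or if it becomes serious. Do not count continuation records of lower intensity or of a step-down from serious. This brings the extra counts above to zero.

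**Separately:** reconcile Protocol 10.5.1 (and 10.4.1) with 10.5.4 and 10.5.5, so that an abnormality that worsens after randomization has a recorded clinical date of worsening. That date should not come from the eCRF audit trail, which under Protocol 15.2 holds the date of the database edit.

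**Cost:** plan wording, record-linking code, review of a few ambiguous links, and one clarified recording instruction. Visits and treatment are unaffected.
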